5 SAFETY ASSESSMENTS

Safety data will be summarized by treatment arm based on the Safety Population.

Adverse events (AEs) will be coded in accordance with the Medical Dictionary for Regulatory Activities (MedDRA 24.1). Severity of AEs will be graded by the investigator according to the National Cancer Institute's Common Terminology Criteria for Adverse Events (NCI-CTCAE), Version 4.03.

The treatment-emergent period is defined as the period of time from the date of the first dose of study treatment up to 30 days after the date of the last dose of study treatment or the day before initiation of subsequent anti-cancer treatment, whichever comes first.

Treatment-emergent adverse events (TEAEs) are those events that occur or worsen during the treatment-emergent period or that are related to the study treatment.

Adverse Events of Special interest (AESI)as listed below will be summarized by treatment arm:

- Protocol-defined events of clinical interest including hemorrhagic events and major hemorrhage.
- Other safety observations including other malignancies (including NMSC, NSC, and MSC), hypertension ("Hypertension" SMQ narrow), interstitial lung disease ("Interstitial lung disease" SMQ narrow), atrial fibrillation (PT = "atrial fibrillation"), cardiac arrhythmia ("Cardiac arrhythmias SMQ, excluding PT of "atrial fibrillation"), Cardiac failure, ventricular tachyarrhythmia ("Ventricular Tachyarrhythmia" SMQ narrow), tumor lysis syndrome ("Tumour lysis syndrome" SMQ narrow), ischemic stroke ("Ischaemic central nervous system vascular conditions" SMQ narrow), sepsis (PTs = "Sepsis", "Bacteraemia", "Fungaemia" or "Septic" (excluding "Septic screen")), cytopenias (PTs="Anemia", "Neutropenia", "Febrile Neutropenia", and "Thrombocytopenia"), infections including viral reactivation (SOC = "Infection and Infestations"), hepatic disorders (SOC = "Hepatobiliary disorders"), embryo-fetal toxicity (SOC = "Pregnancy, puerperium and perinatal conditions"), Diarrhea (PT = "Diarrhoea")

All laboratory values will be converted to and reported as international standard (SI) units. Data for hematology and biochemistry were collected at the respective local laboratories and will be summarized and analyzed by treatment arm. Laboratory parameters will be graded using the NCI CTCAE, Version 4.03. Unless otherwise specified, only baseline and post-baseline values collected during the treatment-emergent period will be included in the safety analysis.

The following safety analyses will be conducted to evaluate the use of venetoclax:

- Infectious pneumonia.
- TLS evaluated by adverse events of special interest and laboratory TLS per Howard criteria.
- Liver function abnormalities evaluated by laboratory data per Hy's law.
- GI Toxicities: No pooling will be done for diarrhea, nausea, and vomiting.
 - For each of the three preferred terms, events leading to treatment discontinuation and dose modification (dose reduction and/or dose hold) will be summarized.

 Table 3
 Summary of Safety Assessments

Assessment Type		
AE	TEAEs, SAEs, Grade 3 or higher TEAEs, related TEAEs, TEAEs leading to treatment discontinuation, TEAEs leading to dose reduction or dose hold, TEAEs leading to death, protocol-defined events of special interest defined by SMQ terms and other safety observations	Descriptive summary statistics and/or listings
Laboratory Parameters	Worst post-baseline toxicity grade for CTCAE-gradable hematology and chemistry results. Abnormalities in creatinine clearance, uric acid levels, and liver function tests. Laboratory TLS per Howard Criteria	Descriptive summary statistics and/or listings
Vital Signs and other Observations Related to Safety	Blood pressure, heart rate, temperature, and body weight, new or worsened eye-related symptoms	Descriptive summary statistics and/or listings

AE: adverse event; CTCAE: Common Terminology Criteria for Adverse Events; SAE: serious adverse event; TEAE: treatment-emergent adverse event; SMQ: standardized MedDRA (Medical Dictionary for Regulatory Activities) query.

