1.1.3 Treatment Time and Follow-up Time

Safety Run-in subjects and TN subjects will be treated with ibrutinib and venetoclax, and randomized subjects will be treated with ibrutinib and venetoclax or ibrutinib and placebo for approximately 104 weeks followed by ibrutinib monotherapy on both treatment arms until progressive disease (PD), unacceptable toxicity or withdrawal of consent. Venetoclax and placebo will be discontinued after 104 weeks of treatment regardless of response assessment.

All enrolled subjects who discontinue study treatment for any reason will be followed for progression (if they have not progressed before treatment discontinuation), subsequent anticancer therapy and survival status until study closure.

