2 GENERAL ANALYSIS CONSIDERATION

The statistical analysis sections in this SAP are mainly for the double-blind Randomization Phase. All data collected for the subjects in the SRI portion will only be summarized with descriptive statistics or listed separately from Phase 3 data. In addition to standard summaries for TEAEs, the safety summary included for SRI subjects will be limited in scope to DLTs and TLS.

Subjects in the randomization phase will be analyzed and summarized by treatment as randomized for efficacy endpoints and as treated for safety.

Subgroup analyses are mainly to evaluate trend and assess the internal consistency of any treatment benefit and/or safety signal. Forest plots of hazard ratios and associated confidence intervals will be provided for each category of the subgroup variable to show the trend. Statistical tests will not be performed for the subgroup analysis.

General Definitions:

The date of the first dose of study treatment is defined as the date the subject received the first dose of ibrutinib or venetoclax/placebo (whichever occurs first), and the date of the last dose of study treatment is defined as the date the subject received the last dose of ibrutinib or venetoclax/placebo (whichever occurs later).

Unless otherwise specified, the baseline value is defined as the last non-missing valid value collected prior to the first administration of study treatment. For subjects who have been randomized but not treated, the randomization date will be used as the reference date for the baseline.

For the Safety Run-in Period, the TLS/DLT assessment period is defined as the standard Ramp-up Period with a minimum of 5 weeks. The DLT period ends on the 7th day of 400 mg venetoclax.

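### The venetoclax-directed pneumonia, liver and GI safety summaries in SAP Section 5 have no venetoclax/placebo exposure window, so they mix combination time with ibrutinib-only time

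*SAP*

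**What the plan says.** Section 5 of the SAP lists infectious pneumonia, TLS, liver abnormalities per Hy's law and GI toxicities under the sentence "The following safety analyses will be conducted to evaluate the use of venetoclax". For diarrhea, nausea and vomiting it also summarises events that led to treatment discontinuation or dose modification.

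The same section defines a single treatment-emergent period, running "from the date of the first dose of study treatment up to 30 days after the date of the last dose of study treatment", or to the day before new anti-cancer treatment if that comes first. Section 2 (General Definitions) fixes the last dose as "the date the subject received the last dose of ibrutinib or venetoclax/placebo (whichever occurs later"). Laboratory data follow the same window: unless otherwise specified, "only baseline and post-baseline values collected during the treatment-emergent period will be included in the safety analysis".

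The two drugs do not stop together. SAP 1.1.3 says "Venetoclax and placebo will be discontinued after 104 weeks of treatment regardless of response assessment", and treatment is then "followed by ibrutinib monotherapy on both treatment arms until progressive disease (PD), unacceptable toxicity or withdrawal of consent". Protocol 5.4 also lets a subject who drops one of the two drugs for tolerability remain in the study on the other.

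Neither document defines a window tied to venetoclax/placebo exposure.

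**The concern.** The stated purpose of the list and the window behind it do not match. A subject who stops venetoclax/placebo, at week 104 or earlier, and stays on ibrutinib keeps contributing to summaries described as evaluating venetoclax.

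This matters because ibrutinib alone produces the listed events. Protocol 1.2.4.11 names diarrhea as the most frequently reported non-hematologic AE with ibrutinib, and Protocol 1.2.3.1 lists pneumonia among the most frequent Grade 3 or 4 and serious events on ibrutinib monotherapy. Ibrutinib-only time adds background events to both arms. It adds more to the combination arm if that arm stays on ibrutinib longer, as the design assumes.

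The GI item needs no model. After venetoclax/placebo has ended, a discontinuation or dose change for diarrhea, nausea or vomiting can concern only ibrutinib, yet it is still counted in the venetoclax list.

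**Working it through.** **Reproducing the plan's own figure.** The documents state no figure for time off venetoclax/placebo, so the check starts with the design that supplies the PFS medians. For 134 events, HR 0.61 and one-sided alpha 0.025, the Schoenfeld formula gives power = Φ(√(134/4) × |ln 0.61| − 1.96) = 81.6%, against the stated approximately 80%. Freedman's formula gives 134 events for 80% power. The design reproduces.

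**Inputs.**
- Median PFS 14 months (control) and 23 months (combination): SAP 1.4.1.
- 260 subjects, 1:1, accrual over about 21 months: SAP 1.4.1. Accrual is assumed uniform.
- Venetoclax/placebo stop at T = 104 weeks = 728 days ÷ 30.44 = 23.9 months: SAP 1.1.3.
- Cut-offs D: 40 months, the projected primary analysis, and 57 months, the projected final OS analysis (SAP 1.4.2); 81 months = 21 + 60, the latest final OS trigger (SAP 1.5.2); and about 33.4 months, when this model reaches the 150 PFS events of SAP 1.5.1.
- Assumption: time on ibrutinib is exponential with the PFS median, ending only at PD, death or cut-off.

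**Formulas.** Let λ = ln 2 ÷ median, and let follow-up F be uniform from D − 21 to D.
- Mean on-treatment time = average over F of (1 − e^(−λF)) ÷ λ.
- Mean on-treatment time after T = average over F of (e^(−λT) − e^(−λF)) ÷ λ where F > T, otherwise 0.
- Share = the second divided by the first.

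**Results (months per subject).**

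| Cut-off | Control: after T / total | Share | Combination: after T / total | Share |
|---|---|---|---|---|
| 33.4 | 0.56 / 13.4 | 4.2% | 0.95 / 16.3 | 5.8% |
| 40 | 1.47 / 15.3 | 9.6% | 2.56 / 19.3 | 13.3% |
| 57 | 4.07 / 18.1 | 22.5% | 7.83 / 24.9 | 31.5% |
| 81 | 5.54 / 19.6 | 28.3% | 12.11 / 29.2 | 41.5% |

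The arms differ because e^(−λT), the proportion still on treatment at week 104 if followed that long, is 30.6% in control and 48.6% in combination.

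**Sensitivity.**
- Allowing a 30-day tail after week 104, the 40-month shares are 8.2% vs 11.5%.
- Adding discontinuation for other reasons at 30% per year, they are 5.6% vs 8.0% at 40 months and 14.7% vs 22.7% at 81 months.
- Adding discontinuation of venetoclax/placebo alone at 10–20% per year in both arms, they are 16.7–23.7% vs 20.7–27.9% at 40 months. The documents give no rate for either kind of discontinuation.
- The cut-off is itself uncertain: at 40 months this model expects about 174 PFS events, not 134 or 150.

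**Effect of ending the window with venetoclax/placebo (no tail).** Mean analysed time, control and combination, goes from 15.3 and 19.3 to 13.8 and 16.7 months at 40 months (arm ratio 1.26 to 1.21). At 81 months it goes from 19.6 and 29.2 to 14.0 and 17.0 (ratio 1.49 to 1.22).

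**The case against.** The strongest reply is that the summaries still answer a legitimate question. Ibrutinib is given in both arms under blinded random allocation with the same 104-week cap, so a whole-period difference describes the effect of adding venetoclax to ibrutinib. The tables are descriptive (SAP Table 3), with no formal safety testing (Protocol 10.6), and the window follows the protocol's own later-of-two-drugs definition. All of this stands. The point concerns interpretation, not an invalid test.

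Share of time also overstates share of events, because AEs are counted as subjects with at least one occurrence. As an illustration, assume constant rates, a rate ratio of 1.5 on venetoclax and 1.0 afterwards. With 11.5% of time off venetoclax, the pooled ratio is 0.885 × 1.5 + 0.115 × 1.0 = 1.44. That is mild dilution.

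Some drug-specific information is already planned: SAP 3.1 tabulates disposition for each study drug, and SAP 3.4 summarises AE-driven reductions and holds for each. Neither is broken down by GI term, so the gap is only partly covered.

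Finally, a window ending with venetoclax/placebo truncates at a post-randomisation event. If venetoclax is stopped for toxicity more often than placebo, that arm loses more observation. This stands too, and is why the added window should not replace the existing one.

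**Conclusion.** The mismatch is on the page: the pneumonia, Hy's law and GI summaries meant to evaluate venetoclax run through ibrutinib-only time, and late GI actions on ibrutinib are counted among them. On the planned medians and uniform accrual, about 10% (control) vs 13% (combination) of on-treatment time falls after week 104 at the 40-month primary analysis, or about 4% vs 6% if 150 events come near month 33. The shares become substantial, 23% vs 32% to 28% vs 42%, only at 57 to 81 months, the period of the final OS analysis and its CSR addendum. Discontinuation for other reasons lowers them; stopping venetoclax/placebo alone raises them.

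Three stronger inferences are not supported:
- A reader might infer that a large part of the time analysed at the primary analysis is off venetoclax/placebo. That would follow from giving every subject long, fixed follow-up. With 21-month accrual, follow-up at month 40 runs from about 19 to 40 months, and the gap between arms is under 4 percentage points. Only an assumed, undocumented rate of early venetoclax/placebo discontinuation pushes the shares much higher.
- A reader might infer that the comparison is invalid. The effect is modest dilution and somewhat unequal observation time in descriptive tables.
- A reader might extend the point to TLS. Laboratory TLS per the Howard criteria is limited to 7 days after the start of therapy (Protocol Appendix G), and Protocol 1.3.3.1 places the risk in the five-week ramp-up.

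**What to change.** In SAP Section 5, keep the whole-period summaries as they are. For infectious pneumonia, Hy's law and GI events, add a supplementary summary by arm from first dose to 30 days after the last venetoclax/placebo dose, capped at the start of subsequent anti-cancer therapy. In the GI item, attribute each discontinuation or dose modification to the drug acted on. TLS needs no change.

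Exposure-adjusted rates over the whole window would correct for unequal time, but would still average combination and ibrutinib-only periods in different proportions by arm, so they do not substitute for the added window.

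The cost is SAP wording, one extra analysis flag and a few tables. The per-drug dosing information is already used in SAP 3.1 and 3.4. Because the added window ends at a post-randomisation stop that may differ by arm, the SAP should say that it is to be read beside the whole-period summary.

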1.3.3.2 Neutropenia

Neutropenia is an important identified risk for venetoclax. Clinical data from the oncology studies suggest that the neutropenia adverse events are observed among subjects who receive venetoclax as a single agent or in combination with other therapeutic agents, with slightly higher frequency observed in some combination studies. Serious adverse events of neutropenia or neutropenia events that lead to discontinuations are few across the entire venetoclax oncology program. For the oncology studies, neutropenia management guidelines are provided in the protocol. Granulocyte colony stimulating factors can be used for supportive measures, however the guidance for their use in non-CLL indications, especially in AML, is per routine local oncology practice, as well as protocol-specific.

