4.1.1 Inclusion Criteria

Prior to enrollment, each potential subject must satisfy all of the following inclusion criteria. These criteria must continue to be met by the subject prior to first dose of study treatment.

Disease-Related

- 1. Pathologically confirmed MCL (tumor tissue), with documentation of either overexpression of cyclin D1 in association with other relevant markers (eg, CD19, CD20, PAX5, CD5) or evidence of t(11;14), as assessed by cytogenetics, fluorescent in situ hybridization (FISH), or polymerase chain reaction (PCR)
 - A report from the local laboratory is acceptable if available; however, it must be reviewed and approved by the central pathology laboratory to verify the above criteria prior to randomization (for Randomization Phase subjects only).
 - If the report from the local laboratory is not available prior to randomization (for Randomization Phase subjects only), the tumor block or slides must be sent to the central pathology laboratory for confirmation of the MCL diagnosis.
- 2. At least 1 measurable site of disease that is ≥ 2.0 cm in the longest diameter and measurable in 2 perpendicular dimensions per CT
- 3. At least 1, but no more than 5, prior treatment regimens for MCL including at least 1 prior rituximab/anti-CD20 containing regimen
- 4. Failure to achieve at least partial response (PR) with, or documented disease progression after, the most recent treatment regimen
- 5. Subjects must have adequate fresh or paraffin embedded tissue (Section 7.1.3.4).

Laboratory

- 6. Adequate hematologic function independent of transfusion and growth factor support for at least 7 days prior to first dose (Safety Run-in Period) or to randomization (for the Randomization Phase), with the exception of pegylated G-CSF (pegfilgrastim) and darbepoeitin which require at least 14 days prior to the first dose (Safety Run-in Period) or to randomization (for the Randomization Phase), defined as:
 - Absolute neutrophil count (ANC) $> 1000 \text{ cells/mm}^3 (1.0 \text{ x } 10^9/\text{L})$
 - Platelet count $> 50,000 \text{ cells/mm}^3 (50 \text{ x } 10^9/\text{L})$
 - Hemoglobin > 8.0 g/dL

Note: Subjects in the Randomization Phase with bone marrow involvement may be enrolled without meeting the above hematologic function criteria after documented discussion with the medical monitor.

- 7. Adequate hepatic and renal function defined as:
 - Serum aspartate transaminase (AST) or alanine transaminase (ALT) \leq 3.0 x upper limit of normal (ULN)

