5.3.1.4 Dose Modification for Adverse Reactions

Ibrutinib interruption and/or dose reduction may be required for toxicities related to ibrutinib. The dose of study drug must be modified according to the dose modification guidance in Table 1 and Table 2 if any of the following ibrutinib related toxicities occur:

- Grade 3 or greater neutropenia with infection or fever
- Grade 4 neutropenia (ANC $< 500/\mu$ L) for more than 7 days. See Section 6.1 for instructions regarding the use of growth factor support.

- Grade 3 thrombocytopenia (platelets $< 50,000/\mu L$) in the presence of Grade ≥ 2 bleeding
- Grade 4 thrombocytopenia (platelets < 25,000/μL)
- Grade 3 or greater non-hematological toxicity (Note: Table 2 recommendations for Grade 3 or greater cardiac failure and cardiac arrhythmias)
- Grade 2 cardiac failure (Table 2)
- Any other Grade 4 or unmanageable Grade 3 toxicity

If clinically indicated, the use of anticoagulants or antiplatelet agents may be considered for the thromboprophylaxis of atrial fibrillation (Section 6.2.4 and Section 1.2.4.6).

For other AEs including grade 2 AEs that are deemed per the investigator potentially manageable by dose reduction, these can be managed with a one dose level dose reduction.

In the event that the investigator feels deviation from the recommendations above is required, please consult the medical monitor to discuss for approval.

Dose changes must be recorded in the Dose Administration eCRF.

Table 1. Ibrutinib Dose Modifications

Hematologic AEs			
Occurrence	Action to be Taken		
First	Withhold ibrutinib until recovery to an ANC \geq 750/ μ L or platelets \geq 25,000/ μ L with no evidence of Grade \geq 2 bleeding; may restart at original dose level		
Subsequent	Withhold ibrutinib until recovery to an ANC $\geq 750/\mu L$ or platelets $> 25,000/\mu L$ with no evidence of Grade ≥ 2 bleeding; may restart at 1 dose level lower* (refer to Table 3)		
Other Hematologic and Non-Hematologic AEs (for Events not Specified in Table 2)			
Occurrence	Action to be Taken		
First	Withhold ibrutinib until recovery to Grade ≤ 1 or baseline; may restart at original dose level ^a		
Second	Withhold ibrutinib until recovery to Grade ≤ 1 or baseline; restart at 1 dose level lower* (3 capsules [ie 420 mg daily]) (refer to Table 3)		
Third	Withhold ibrutinib until recovery to Grade ≤ 1 or baseline; restart at 1 dose level lower (2 capsules [ie 280 mg daily]) (refer to Table 3)		
Fourth	Discontinue ibrutinib		

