Laboratory tests will be summarized separately for hematology and serum chemistry. All laboratory values will be graded using the CTCAE v4.03. The worst toxicity grade for selected laboratory tests will be tabulated.

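### Laboratory Grade 3-4 cytopenia is tabulated without reference to baseline, although subjects with marrow involvement may enter with platelets already below the protocol's Grade 3 boundary

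*SAP*

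**What the plan says.** SAP Section 5, Table 3, plans for hematology and chemistry: "Worst post-baseline toxicity grade for CTCAE-gradable hematology and chemistry results". Protocol 10.6 is no more specific: "The worst toxicity grade for selected laboratory tests will be tabulated". Neither document names a shift table, a baseline-by-worst-grade table or a worsened-from-baseline rule for laboratory grades, and SAP Section 7 lists no change on this point. SAP Section 5 admits baseline laboratory values to the safety analysis but names no graded output that uses them.

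Adverse events are treated differently. SAP Section 5 states: "Treatment-emergent adverse events (TEAEs) are those events that occur or worsen during the treatment-emergent period", and then also admits events related to study treatment. Table 3 itself limits eye symptoms to new or worsened ones.

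Protocol 4.1.1, criterion 6, sets entry limits of ANC above 1000, platelets above 50,000 and hemoglobin above 8.0 g/dL. Its Note then says: "Subjects in the Randomization Phase with bone marrow involvement may be enrolled without meeting the above hematologic function criteria after documented discussion". The medical monitor is the other party to that discussion, and the Note gives no lower bound. Protocol 5.3.1.4 places Grade 3 thrombocytopenia below 50,000 and Grade 4 neutropenia below 500.

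**The concern.** A worst post-baseline grade measures on-treatment toxicity only if subjects start below the grade being counted. The waiver means some may not. Protocol 1.1.1 describes marrow as a frequent extranodal site in this disease, so the group to whom the Note could apply is not a rare one. A waived subject with platelets below 50,000 who stays there after dosing enters the Grade 3-4 row even though nothing has changed.

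The added subjects are expected in equal proportion in both arms, so they raise both rates and compress the ratio. That matters most for the toxicity the added drug is expected to cause: Protocol 1.3.3.2 says "Neutropenia is an important identified risk for venetoclax". Safety is descriptive, with no formal testing (Protocol 10.6), so readers will judge the added hematologic toxicity from the tabulated rates.

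**Working it through.** **Can a subject start at Grade 3-4?**

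- Platelets: the waivable limit is 50,000 and the Grade 3 boundary in Protocol 5.3.1.4 is the same figure. A subject admitted below it is at Grade 3 or worse.
- Neutrophils: Grade 4 is below 500. The waiver has no floor, so this is possible. The Grade 3 boundary for ANC is not stated in the documents.
- Hemoglobin: no grade boundary is stated in the documents, so no match can be shown.

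**How much could it move the table?** The plan gives no figure to reproduce. Let b be the share of each arm that is Grade 3-4 at baseline and still so after dosing, and p the rate of new Grade 3-4 among the rest. The planned table shows

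observed rate = b + (1 − b) × p.

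The values of b and p are assumptions; the documents give none of them. Take p = 45% versus 25% (ratio 1.80, difference 20 points):

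| b | Combination | Control | Ratio | Difference |
|---|---|---|---|---|
| 0 | 45.0% | 25.0% | 1.80 | 20 points |
| 5% | 0.05 + 0.95 × 0.45 = 47.75% | 0.05 + 0.95 × 0.25 = 28.75% | 1.66 | 19 points |
| 10% | 0.10 + 0.90 × 0.45 = 50.5% | 0.10 + 0.90 × 0.25 = 32.5% | 1.55 | 18 points |

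The difference shrinks only by the factor (1 − b). With about 130 subjects per arm (260 randomized 1:1), b = 5% is 130 × 0.05 = 6.5 subjects per arm and b = 10% is 13.

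**Rarer events.** With assumed rates of 20% versus 10% (ratio 2.00), the ratio becomes 1.83 at b = 2%, 1.66 at 5% and 1.47 at 10%. Dilution of the ratio is stronger when the event is rarer.

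**Incomplete persistence.** Now let b be the baseline Grade 3-4 share and c the fraction of it still Grade 3-4 after dosing, with the recovered remainder at risk at rate p. The observed rate is b × [c + (1 − c) × p] + (1 − b) × p. For b = 5% and 20% versus 10%:

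- c = 0.8: 23.2% / 13.6% = 1.71
- c = 0.5: 22.0% / 12.25% = 1.80

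**Chance imbalance.** Randomization is not stratified by marrow involvement or baseline counts. In 200,000 simulated trials of 130 per arm (b = 5%, 20% versus 10%), the planned ratio was below the new-onset ratio in 88%. Over a grid with control rates of 5-20%, true ratios of 1.5-2.0 and b of 2-15%, this ranged from 64% to 99%.

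**After the fix.** Counting only subjects below Grade 3 at baseline removes b. For 20% versus 10% and b = 5%, 130 × 0.95 = 123.5 are at risk per arm, with 24.7 versus 12.35 expected events, ratio 2.00.

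**The case against.** The strongest reply is that cytopenias are assessed elsewhere. SAP Section 5 makes them an adverse event of special interest by arm. Table 3 adds Grade 3 or higher TEAEs and events leading to dose reduction or hold, and the TEAE rule already requires onset, worsening or relatedness. This stands in part: the gap is in the laboratory table, not in all cytopenia reporting, and a reader should not infer that worst grade is the only look at cytopenia. But Protocol 7.1.1.5 turns a laboratory change into an AE only under stated conditions. The cytopenia group also uses four preferred terms and omits *neutrophil count decreased* and *platelet count decreased*, which Protocol 1.2.3.2 lists as separate terms. The AE tables therefore do not replace graded laboratory data.

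It may also be said that Table 3 is a summary list, that baseline values are in the safety analysis, and that a shift table can be produced at any time. That is true, and it is why the point is minor. It does not make the stated output the right main summary.

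Three stronger readings are tempting and not supported:

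- **The ordinary entry limits inflate the Grade 3-4 row.** Without a waiver, entry needs platelets above 50,000 and ANC above 1000, and Protocol 4.1.1 requires the criteria still to be met before the first dose. That rules out Grade 3-4 platelets and Grade 4 neutropenia at the start. What the documents show rests on the waiver alone, and it applies only in the Randomization Phase.
- **Chemistry has the same problem because creatinine clearance of 30-60 mL/min is eligible.** The documents give no creatinine grade boundaries and do not tie that range to Grade 3-4. Table 3 also lists creatinine clearance abnormalities separately.
- **The effect is known to be large.** Nothing in the documents supports a particular baseline share, least of all a high one reached through individually discussed waivers.

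**Conclusion.** The point holds for hematology, as a minor improvement to a descriptive safety output. The planned table counts persisting pre-existing low counts as on-treatment Grade 3-4. The documents demonstrate this for platelets, and for neutrophils at Grade 4. In expectation it overstates absolute rates in both arms and moves a ratio above 1 toward 1; in a single trial, chance imbalance could push the ratio either way.

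The illustration (1.80 becoming 1.66 or 1.55, and 20 points becoming 19 or 18) rests on assumed rates, an assumed 5% or 10% share equal in both arms, and full persistence after dosing. Less persistence means less dilution. If few waivers were granted, the effect is close to nil. No efficacy result or formal test depends on it.

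**What to change.** In SAP Table 3, laboratory row, add by treatment arm:

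1. A shift table of baseline grade by worst post-baseline grade for neutrophils, platelets and hemoglobin.
2. As the main Grade 3-4 summary, the number and percentage with new Grade 3-4 among subjects below Grade 3 at baseline.

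State one rule for a missing baseline, for example to exclude the subject from the denominator and report how many were excluded. Keep the worst post-baseline grade table as a supplement.

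The second summary does not count a subject who moves from Grade 3 to Grade 4. The shift table shows those subjects, which is why both are needed. A simple worsened-from-baseline count over all subjects would instead keep baseline Grade 4 subjects in the denominator although they cannot worsen.

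The cost is a little programming and a slightly smaller denominator. Baseline is already defined in SAP Section 2, and hematology is collected at Screening and Week 1 Day 1 (Protocol Appendix A). No eligibility rule, treatment rule or data collection changes.
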